7 STUDY PROCEDURES

7.1 Subject Recruitment and Pre-Screening

Persons scheduled for elective total hip arthroplasty will be approached and screened by a Principal Investigator, nurse or research staff for suitability for this study. Persons who meet all of the inclusion and none of the exclusion criteria will be asked if they are interested in participating in the study. A subject is considered enrolled in the study once the subject's written informed consent has been documented. Consent may be obtained pre-surgery.

If the subject signs the Informed Consent form and is identified later as failing to meet all eligibility criteria, the subject will be classified as a screen failure. Upon determination that the subject does not meet all eligibility criteria, the reason for the subject's ineligibility will be documented on the Screening and Enrollment Log for the study. In the event that a subject leaves the study prematurely or is withdrawn from the study, another subject may be recruited.

A partial waiver of HIPAA authorization is being requested for the pre-screening process for this study. The pre-screening process would require study personnel to access personal health information to identify prospective subjects without HIPAA authorization, and this would occur prior to introducing them to the study or obtaining informed consent. Informed consent and HIPAA authorization will be obtained for all patients who are interested in participation; however, the pre-screening process would require a partial waiver of HIPAA authorization, as the research study could not be practically carried out without this partial waiver of authorization. The participants' rights and welfare are not adversely affected by the waiver. Patients' protected health information (PHI) will not be inappropriately reused or disclosed to any other person or entity. To further safeguard all protected health information, the data collected for the purposes of this study will not be labeled with any personal identifying information, or with a code that can be linked to personal identifying information. The data will not be stored with any protected health information identifiers.

7.2 Informed Consent Process

The Investigator(s) and/or staff delegated for this task are responsible for conducting the informed consent process and for obtaining written informed consent and the HIPAA/data protection authorization from each potential subject before any study-specific procedures required by the clinical protocol are performed. The Investigator shall not allow subjects to participate in the study or consent any subjects prior to receiving IRB approval of the consent process.

Informed consent should be obtained in written format and using a form approved by the local IRB and Sponsor in accordance with applicable federal and provincial regulations. The informed consent may be signed on paper or electronically, as approved by the IRB. The informed consent process may be conducted remotely via videoconference (Zoom, Teams, etc.). After a patient is deemed eligible from the screening process, study team members will approach the patient or schedule a videoconference to explain the study. If the consenting will be conducted remotely, the informed consent document shall be securely provided to the subject prior to the scheduled videoconference. The study staff will thoroughly explain the purpose, procedures of the study in respect to subject's involvement and responsibilities, potential risks and benefits, subject's rights and privacy of the data collected. In addition to the full disclosure of the risks and benefits of participating in the study, patients will be informed that their participation is voluntary and their decision will not impact patient care. They will be given adequate time to ask questions regarding the study and to discuss with family and friends before making the decision. At this point the subject will be asked to sign the research consent form. If consent is being obtained remotely, consents will be signed electronically using an e-signature service such as Adobe sign, DocuSign, etc. by both the subject and the person obtaining consent.

All signed consent and HIPAA forms will be kept at the site and are only accessible to study team members. If the patient refuses to participate, the patient will not be enrolled in this study. The original signed consent will be filed in a secure, locked cabinet with the subject's other original study documents. A copy of the signed consent should be filed in the hospital/clinical chart. A copy of the signed consent and HIPAA/data protection authorization must be provided to the subject. The Principal Investigator (PI) is responsible for ensuring any new information related to the study will be provided to the subject. The subject may need to be re-consented to continue participation, if required by the IRB.

The subject will be assigned a non-identifying subject number for the data collected in this study. The Investigator shall retain a copy of the signed informed consent document in each subject's record. The subject shall be provided with a copy of the signed informed consent document.

7.3 Study Procedures

Study procedures will be conducted according to the schedule outlined in Table 1 below and recorded in REDCap. See Appendices for scales, questionnaires, and assessments to be used in the study. Any adjustments to or replacements of these appendices will be justified with documentation in study files.

A 10x10 grid of black and white squares. The first two columns are black, followed by a 3x3 block of white squares. The next two columns are black, then a 3x3 block of white squares, and finally two black columns. The pattern repeats vertically.

7.3.1 Preoperative

During the pre-operative period, the Investigator and/or staff delegated for this task shall verify eligibility criteria for the subject. If the subject does not meet all eligibility criteria and they have already been enrolled into the study, they will be notified and removed from the study. As part of the eligibility screening, subjects with a PROMIS Anxiety raw score of >19 will be removed from the study.

Following written consent the subject's demographic information, including but not limited to, age, weight, height, race, and ethnicity will be recorded on the CRF. In addition, a complete medical, vital signs, medication (including opioids), and surgical history, family medical history (chronic pain, addiction, cardiac, cancer, etc) EKG, PROMIS (Patient-Reported Outcomes Measurement Information System) assessments covering anxiety, depression and pain catastrophizing may be captured.

A series of 3 horizontal black bars of varying lengths, likely representing data points or measurements. The bars are arranged vertically, with the longest bar at the top and the shortest at the bottom. Each bar has a small white gap before the next one begins.

7.3.2 Intraoperative

The surgery will be performed under spinal plus sedation. Intraoperative patient management will be according to standard of care protocol.

7.3.3 Postoperative

Once the surgery is over and the patient is transferred to the recovery room, the patient will continue to receive postoperative pain control per standard of care, as determined by the anesthesia and surgical teams. Research assessments that will be collected by the research team will include [REDACTED]

[REDACTED]
[REDACTED]
[REDACTED]
[REDACTED]
[REDACTED]

7.3.4 Blinding and Randomization**7.3.4.1 Subjects will be randomized at point of enrollment.**

[REDACTED]
[REDACTED]
[REDACTED]
[REDACTED]
[REDACTED]
[REDACTED]
[REDACTED]

7.3.4.4 Unblinding subject's treatment assignment to the entire study staff will only be done when necessary (i.e. for the treatment of an adverse event).

[REDACTED]
[REDACTED]
[REDACTED]
[REDACTED]
[REDACTED]
[REDACTED]

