2.1 Bridge (active) vs. Sham device

Bridge is a device that electrically stimulates branches of Cranial Nerves V, VII, IX and X, and the occipital nerves identified by transillumination through percutaneous electrodes.

The components of the Bridge device include the following:

- Percutaneous electrical nerve field stimulator (PENFS) system
- Multi-pin wire harness percutaneous electrode
- Pen light for use in the transillumination technique that aids in positioning of the percutaneous electrodes

The wire harness percutaneous electrode array consists of 4 leads. The 1-1-1-4 configuration consists of three single-needle leads, and one 4-needle array. The stimulator is placed behind the ear and percutaneous electrodes are positioned utilizing the transillumination function of the device. The transillumination technique assists in the visualization of neuro-vasculature matrixes, to aid in the placement of the percutaneous electrodes near the nerve branches in the ear. The Bridge device has a 120 hour run-time and has a pulse sequence of 2 hours on and 1 minute off with the cycle repeating over the 120 hour run-time.

The sham device has the same appearance and will require the same placement technique as the Bridge (active) device but will not deliver electrical impulses.

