4.1 Study Arms

4.1.1 Treatment Arm

Bridge auricular therapy will be given in addition to standard of care. Research coordinators that have been trained in placing the Bridge device will apply the device in the immediate post-operative setting (post-anesthesia care unit, PACU). The device will be attached according to the instructions for use provided. Pain scores using a numerical scale will be collected at rest and movement, as well as total opioid consumption and the device tolerability.

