4.1.2 Control Arm

Same treatment as in the active arm with the only exception being the use of a sham Bridge device. The sham Bridge device will be identical in appearance to the active device but will have no electrical current and no electrode needles.

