8.3 Definitions

The definitions for adverse event, adverse device effect, serious adverse event, serious adverse device effect, and unanticipated adverse device effect are provided below (ISO 14155:2011, 21 CFR 812.3(s)).

- Adverse Event (AE): an adverse event is any untoward medical occurrence in a subject which need not be related to the device under investigation.
- Adverse Device Effect (ADE): an adverse device effect is any untoward or unintended response to a medical device which may result from insufficiencies in the instructions for use or deployment of the device, or from use error.
- Serious Adverse Event (SAE): a serious adverse event is an adverse event that results in death, inpatient hospitalization, severe or permanent disability, a life threatening illness or injury, fetal distress, fetal death, a congenital abnormality, a birth defect, or medical or surgical intervention to prevent permanent impairment to body or structure.
- Serious Adverse Device Effect (SADE): a serious adverse device effect is an adverse device effect that results in death, inpatient hospitalization, severe or permanent disability or is life threatening.
- Unanticipated Adverse Device Effect (UADE): any serious adverse effect on health or safety or any life threatening problem or death caused by or associated with, a device, if the effect, problem, or death was not previously identified in nature, severity or degree of incidence in the investigational plan, or application (including a supplementary plan or application) or any other unanticipated serious problem associated with a device that is related to the rights, safety or welfare of subjects. Refer to the Device Risk Analysis and Risk Assessment section for details on anticipated adverse device effects.

8.4 Anticipated Adverse Events:

- Bleeding or infection at the puncture site
- Skin irritation
- Pain at the site of application
- Allergic contact dermatitis to the compound benzoin tincture.

8.5 Adverse Event Reporting:

- All Adverse Events, both Anticipated and Unanticipated, must be recorded within the CRF on the Adverse Event Report Form.
- All Adverse Events must be promptly reported to the Sponsor.
- All Unanticipated Adverse Device Effects will be also reported to both the Sponsor and the IRB.
- Both Serious Adverse Events and Unanticipated Adverse Device Effects must be reported to the Sponsor within 48 hours. All other Adverse Events should be reported to the Sponsor within 5 business days.

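### Section 7.3.4.4, as visible, lets an emergency unblinding reach all study staff, including those still collecting that subject's outcomes (minor)

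*Combined protocol and SAP*

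**What the plan says.** Section 7.3.4.4 states that unblinding a subject's "treatment assignment to the entire study staff will only be done when necessary (i.e. for the treatment of an adverse event"). It is the only readable sentence on unblinding. Sections 7.3.4.2 and 7.3.4.3 and the text after 7.3.4.4 are blacked out.

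Four other places bear on who is told and what they still have to measure:

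- **Outcome collection.** Section 7.3.3 begins its list with "Research assessments that will be collected by the research team will include" (the list itself is redacted). Section 4.1.1 names the content: "Pain scores using a numerical scale will be collected at rest and movement, as well as total opioid consumption and the device tolerability".
- **Follow-up.** Section 7.3.8 plans phone contacts at one week and one month without naming the caller. The lost-to-follow-up definition in Section 6.5 makes study staff the people who try to reach the subject.
- **Device and sham.** Section 4.1.1 says "Research coordinators that have been trained in placing the Bridge device will apply the device in the immediate post-operative setting". Section 4.1.2 says the sham "will have no electrical current and no electrode needles", while Section 2.1 says "The sham device has the same appearance and will require the same placement technique as the Bridge (active) device".
- **Anticipated events.** Section 8.4 lists "Bleeding or infection at the puncture site", skin irritation, pain where the device is applied, and "Allergic contact dermatitis to the compound benzoin tincture".

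**The concern.** Treating one subject's adverse event may require the people treating it to know the assignment. It does not require the people who ask for pain scores, record opioid use or make the follow-up calls to know it. The readable rule draws no such line, and the group it names appears to include them.

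Pain and tolerability are subjective ratings elicited by staff, some of them by phone. A collector who knows the arm can influence how a question is put or an answer recorded. In a sham-controlled trial of up to 60 subjects, blinded collection is a main protection for such endpoints. If unblinding were also more frequent in one arm, the influence would not be balanced between arms.

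**Working it through.** The documents give no figure for unblinding, so there is nothing to reproduce. The check is a reading of the text, followed by an illustration on assumed rates.

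**Step 1: who is told.** Section 7.3.4.4 names the whole study staff. Section 7.3.3 gives the assessments to the research team. Section 6.5 uses study staff for those attempting follow-up contact. On ordinary reading, the outcome collectors are within the group told.

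**Step 2: whether outcomes remain to be collected.** Section 8.2 has adverse events collected daily for five days, then at one week and one month. The primary endpoints in Section 4.2.1 run from surgery to day 5. Section 8.2 asks for tolerability daily to day 5. The secondary pain and opioid endpoints in Section 4.2.2 run to day 30. An event in the first days can therefore lead to unblinding while primary and secondary data for that subject are outstanding. Assessments made before the unblinding are not affected.

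**Step 3: whether one arm is more exposed.** If Section 4.1.2 governs, puncture-site bleeding or infection cannot come from the sham, so an active-arm excess is plausible. If the sham is placed with the same technique, as in Section 2.1, the asymmetry is less clear. Skin irritation, and benzoin dermatitis if benzoin is also used to attach the sham, could occur in either arm.

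**Step 4: illustration of size.** Assumptions, none from the documents: 1:1 allocation of 60 subjects (30 per arm), unblinding rates pA (active) and pS (sham), and a shift of d points in the recorded 0-10 pain score of each unblinded subject.

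- Expected unblinded subjects = 30 × pA and 30 × pS.
- Chance of at least one = 1 − (1 − pA)^30 × (1 − pS)^30.
- Bias in the mean difference, shift of the same sign in both arms = (pA − pS) × d.
- Size of the bias, shift of opposite sign in the two arms = (pA + pS) × d.

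With d = 1:

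| pA, pS | Expected active, sham | Active share | At least one | Bias, same sign | Bias, opposite sign |
|---|---|---|---|---|---|
| 2%, 2% | 0.6, 0.6 | 50% | 70% | 0.00 | 0.04 |
| 5%, 2% | 1.5, 0.6 | 71% | 88% | 0.03 | 0.07 |
| 10%, 2% | 3.0, 0.6 | 83% | 98% | 0.08 | 0.12 |
| 20%, 5% | 6.0, 1.5 | 80% | over 99% | 0.15 | 0.25 |

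The opposite-sign column is there because a collector who expects the device to work might record lower pain on active and higher pain on sham. Equal rates would then not cancel the bias. A 2-point shift doubles every bias entry.

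The table treats the shift as applying to all of a subject's assessments. If only a fraction f follows the unblinding, each entry is multiplied by f. With f = 0.5, for example, the last row becomes 0.15 × 0.5 = 0.075 and 0.25 × 0.5 = 0.125.

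**The case against.** The strongest objection is that the sentence restricts unblinding. A reader might infer that every adverse event needing treatment unblinds all staff. The text does not say so: necessity is the threshold, and mild skin irritation or site pain would rarely require knowledge of the arm. This part of the objection stands.

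A reader might also infer that unblinding will fall mostly in the active arm. That rests on Section 4.1.2 prevailing over Section 2.1 and on puncture-site events being the ones that lead to unblinding. No event or unblinding rate is given, and two of the listed event types need no puncture. The documents support only that it could be more frequent on active.

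Third, the hidden parts of 7.3.4 may define separate assessors or an unblinding procedure. The reference to all staff may also be meant as a contrast with one person who already knows the arm. It therefore cannot be said that the plan lacks a safeguard. But the readable sentence still offers no step short of telling everyone. If hidden text keeps assessors blinded, the two need reconciling.

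Fourth, if the sham has no needles, the coordinator who applies it can probably already tell the arm, and a visible puncture-site event reveals it to anyone who sees it. That may be a larger threat to blinding than this rule. Narrowing the recipients would not cure it, but it would stop the rule from adding to it.

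Finally, pain is the subject's own rating, and the sentence discloses to staff, not to the subject. This limits the likely shift, though staff still elicit and record the score. It is one reason not to rely on a larger figure such as 0.20 × 2 = 0.40 points, which needs 20% unblinded on active, none on sham, and a 2-point shift across all assessments.

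**Conclusion.** The point holds as a minor one. As visible, 7.3.4.4 allows one subject's assignment, when unblinding is necessary to treat an adverse event, to be given to all study staff. On its face that includes the people who go on to collect that subject's pain, opioid, tolerability and follow-up data.

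The exposure is confined to affected subjects and to assessments made after the unblinding. Under the assumed rates and a 1-point shift, the bias is at most 0.15 points (same sign) or 0.25 points (opposite sign), and both figures need unblinding to be common. These figures rest wholly on assumed rates, an assumed 1:1 allocation and an assumed shift. Nothing was computed for opioid consumption, which Section 8.2 names as the primary outcome, because the documents give no basis for a shift in it.

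**What to change.** Replace the recipient group in 7.3.4.4 with wording such as:

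> When unblinding is necessary, the assignment of that one subject is disclosed only to those treating the event. The clinician decides when it is necessary. Staff who collect pain, opioid, tolerability and follow-up data remain blinded as far as possible. The date, reason and recipients of each unblinding are recorded.

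Then check the sentence against the redacted parts of 7.3.4, so that roles and procedure agree.

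The change does not ask that the person judging relatedness stay blinded. Section 13 has the Principal Investigator evaluate all adverse events, and that person may also be treating the subject.

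The cost is a wording change, a short log, and having the code held by someone who does not collect outcomes. At a small site that last item may need some arrangement of duties.

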7.3.5 Bridge Device Placement

[REDACTED]
[REDACTED]
[REDACTED]
[REDACTED]
[REDACTED]
[REDACTED]
[REDACTED]

7.3.6 Bridge Device Home Instructions

Term	Percentage
GDP	100%
Inflation	98%
Interest rates	95%
Central bank	90%
Monetary policy	85%
Quantitative easing	75%
Inflation targeting	70%
Interest rate hike	65%

7.3.7 Discharge

Term	Percentage
Climate change	95
Global warming	100
Green energy	98
Carbon footprint	92
Sustainable development	88
Renewable energy	90
Emissions reduction	85
Green economy	80
Carbon tax	75

7.3.8 Study Follow-up

Subjects will be contacted via a phone call for follow-up visits at 1 week and 1 month.

For more information, contact the Office of the Vice President for Research and Economic Development at [contact] or [contact].

7.3.9 Study Completion

The subject is considered to have completed the study after they have worn the Bridge device

8 STATISTICAL PLAN

8.1 Sample Size

This study may enroll up to 60 subjects. Descriptive statistics will be presented as mean \pm SD. Continuous variable will be reported as median (95 % confident interval). Using SPSS, a one tailed unpaired t-test will be performed to assess the difference in pain between groups. Overall difference between groups over the 5 days will be assessed using an analysis of variance as follows: by Performance test. [REDACTED]

8.2 Acceptance criteria

The primary outcome measured will be the total opioid consumption for the 5 day period following surgery. Secondary outcome will include pain, PONV, and functional recovery at 24, 48, 72, 96 and 120 hrs post operatively. The subject will be asked to rate the tolerance of the device using a 1-5 scale (1 being extremely poorly tolerated and 5 being extremely well tolerated) every postoperative day until day 5. Safety and Adverse Events not related to the surgery or the hip implant will be collected postoperatively every day for the first 5 days, and at 1 week and 1 month.

8.3 Definitions

The definitions for adverse event, adverse device effect, serious adverse event, serious adverse device effect, and unanticipated adverse device effect are provided below (ISO 14155:2011, 21 CFR 812.3(s)).

- Adverse Event (AE): an adverse event is any untoward medical occurrence in a subject which need not be related to the device under investigation.
- Adverse Device Effect (ADE): an adverse device effect is any untoward or unintended response to a medical device which may result from insufficiencies in the instructions for use or deployment of the device, or from use error.
- Serious Adverse Event (SAE): a serious adverse event is an adverse event that results in death, inpatient hospitalization, severe or permanent disability, a life threatening illness or injury, fetal distress, fetal death, a congenital abnormality, a birth defect, or medical or surgical intervention to prevent permanent impairment to body or structure.
- Serious Adverse Device Effect (SADE): a serious adverse device effect is an adverse device effect that results in death, inpatient hospitalization, severe or permanent disability or is life threatening.
- Unanticipated Adverse Device Effect (UADE): any serious adverse effect on health or safety or any life threatening problem or death caused by or associated with, a device, if the effect, problem, or death was not previously identified in nature, severity or degree of incidence in the investigational plan, or application (including a supplementary plan or application) or any other unanticipated serious problem associated with a device that is related to the rights, safety or welfare of subjects. Refer to the Device Risk Analysis and Risk Assessment section for details on anticipated adverse device effects.

8.4 Anticipated Adverse Events:

- Bleeding or infection at the puncture site
- Skin irritation
- Pain at the site of application
- Allergic contact dermatitis to the compound benzoin tincture.

8.5 Adverse Event Reporting:

- All Adverse Events, both Anticipated and Unanticipated, must be recorded within the CRF on the Adverse Event Report Form.
- All Adverse Events must be promptly reported to the Sponsor.
- All Unanticipated Adverse Device Effects will be also reported to both the Sponsor and the IRB.
- Both Serious Adverse Events and Unanticipated Adverse Device Effects must be reported to the Sponsor within 48 hours. All other Adverse Events should be reported to the Sponsor within 5 business days.
- All Serious Adverse Events will be also reported to the IRB per IRB reporting requirements. These reports may include, but will not be limited to: date of onset; brief description of the events; their treatment; whether they resulted in death, inpatient hospitalization, severe or permanent disability or were life threatening; their relationship to the study device; and resolution.

